5.0 Resources and Personnel

Roles and responsibilities

The **Principal Investigator/Study Chair** ([name]) and **Co-Principal** ([name]), will assume responsibility for all aspects of the conduct of this research study and supervise all Seattle-based personnel. They, along with the site PIs, will be responsible for training research staff, including the VETPALS facilitators, peer facilitators, and site study coordinators. They will also develop the study protocol, operations manual, monitoring plan and have oversight on study monitoring and study steering committee meetings.

Site Principal Investigators (Drs. [name], [name], [name], [name], and [name]) are responsible for operations, data collection, and data integrity at their sites which involves oversight of the site study coordinators and regular meetings to discuss data and operations. They are also responsible for training the research staff at their site, including the VETPALS facilitator, peer facilitator, and site study coordinator. Site PIs, along with VETPALS facilitators,

will contact the data manager to obtain random assignment for participants. Site Principal Investigators may also assist with screening and enrollment as needed at their site.

Co-Investigators ([name] and [name]) will oversee VETPALS facilitator ratings on an ongoing basis to provide corrective feedback to facilitators in real-time along with the PI/SC. They will also lead weekly meetings with the study facilitators to provide ongoing supervision and discuss delivery of the treatment, including the prevention of facilitator drift in the manuals. The Co-Investigators will also assist with tasks as requested by the PI/SC, which include but are not limited to: finalizing the study protocol, overseeing progress at all sites, developing the operations manual and other study SOPs, monitor treatment fidelity by reviewing audio files, running steering committee meetings, and training VETPALS facilitators and peer facilitators.

Co-Investigator [name] was a Co-PI for the original PALS program on which VETPALS is based. He will assist with tasks as requested by the PI/SC and Co-Investigators, which include but are not limited to: training VETPALS facilitators and peer facilitators, revising the treatment manual/participant workbook, interpretation of statistical analysis, and writing manuscripts for publication at the end of the study.

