VETPALS facilitators are allied health professionals who are responsible for implementing the VETPALS intervention group sessions. VETPALS facilitators will be trained by the core group of investigators to deliver a modified version of PALS which reflects changes in content, delivery modalities (e.g. telehealth, video teleconferencing), and participants (Veterans with dysvascular disease/diabetes). VETPALS facilitators will receive training during a two-day group-based training that includes didactics, supervised practice, discussion, and home study. Notably, all VETPALS facilitators have already received initial training the PALS protocol and have advanced Department of Defense (DOD) training and certification in amputation care. VETPALS facilitators are primarily responsible for contacting the data manager to randomize a group of participants, maintaining an accurate randomization log, and conducting the 5 intervention sessions per group of 8 ± 2 participants. The intervention sessions will take place in a private conference room with video teleconferencing capabilities at each VA site. All VETPALS facilitators will participate in ongoing group supervision as part of fidelity monitoring of the intervention, and additional focused instruction will be provided on an individual basis as needed when identified during a review of audio-recorded sessions. VETPALS facilitators may assist with screening and enrollment at their site.

VETPALS peer facilitators are Veterans with limb loss. One peer facilitator at each site will be identified and trained by the VETPALS facilitator. Substitute or alternate peer facilitators may also receive training as needed at each site. The peer facilitator will help co-lead the VETPALS

sessions (as in the original PALS program). The peer mentor will only have study-related contact with participants in the context of the class. The peer will not access the medical record, or engage in other research-related activities. Thus, the peer mentor will not have access to any information about the participant that is not shared directly by the participant during class.

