Enrolled participants are assigned on a rolling basis into successive cohorts of 8±2 individuals at each participating site. Each time 8±2 participants are enrolled, that cohort will be randomized 1:1 to receive either the VETPALS intervention or individual education support program (control condition). We will ensure that participants will not have completed a PALS program prior to study participation and will not be part of an existing PALS group during their study participation. Randomization will occur through an email exchange between the study sites (VETPALS facilitator or site PI) and the data manager at Spectrum Research. The data manager will maintain a randomization table that is stored locally on a server at Spectrum Research. When a cohort is ready for randomization, the facilitator or site PI will send an email to the data manager stating that a group of participants is ready for randomization. The email will also include a list of study ID numbers but will not contain any information that could identify participants. Within 12-24 hours of receiving the email, the data manager will verify the list of study IDs in the database to ensure all baseline assessments are complete, and then will obtain random assignment by accessing the randomization table. The data manager will respond via email to the facilitator or site PI with a value of 0 or 1 (0=individual education support program, 1=VETPALS). Both parties will retain a copy of the email for reference. The data manager will record the treatment assignment for the group in the randomization table, and the facilitator or site PI will record the treatment assignment in the randomization log. This method will ensure that treatment allocation is concealed during the recruitment of each cohort. A balanced number of groups will be randomly assigned to each site based on the projected enrollment at that site, which is a common randomization schedule used in group-based interventions. The randomization schedule and algorithm will not be shared with local sites to maintain concealment of treatment allocation. Additionally, the data manager will record a value of 0 or 1 to each study ID in the database which is linked to the study ID assigned at enrollment. Clinical research staff at each location (applicable investigators and VETPALS facilitators) will receive the treatment allocation and randomization ID in order to proceed with the treatment, intervention or control. Site study coordinators who conduct the baseline and follow-up assessments are blind to treatment.

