Participants will complete follow-up assessments with study coordinators in-person or by telephone at 6 weeks and 6 months. Study coordinators will screen for any anticipated and unanticipated adverse events at scheduled follow-up visits and by telephone contact with participants at 3 weeks and 18 weeks. Coordinators will briefly call participants to check-in, do a few medical review questions, and give a reminder of the next study appointment. Coordinators who cannot reach participants by phone at 3 or 18 weeks for the medical review questions should alert another site researcher who can complete the assessment by medical record review in CPRS. At the end of the study, coordinators will conduct a final 1-year medical record review. Study coordinators do not access the medical record until all follow-ups are complete at the end of the study in order remain blind to intervention assignment.

[figure not shown]
Additional details of the assessments and a study flow sheet can be found in the protocol document. Participants will receive reminders via telephone and mail for upcoming study visits from the study coordinator. The baseline assessment will take up to 60 minutes to complete and follow-up assessments will take up to 30 minutes to complete. Study coordinators remain blinded to treatment condition throughout the entire study and will be trained to ensure consistent and optimal administration of the assessments, as well as on strategies to remain blinded from treatment (e.g. strategies to remind patients not to reveal treatment).

Randomization

As described on page 21, this is a two-arm randomized controlled trial. The treatment allocation will automatically be matched to the study ID in the online randomization system. Clinical research staff at each location (site PIs and VETPALS facilitators) will receive the treatment allocation and proceed with study related activities for both conditions. Again, site study coordinators who conduct the baseline and follow-up assessments are blind to treatment.

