- Once a group of 8 participants (± 2 when necessary) complete the baseline assessment, the coordinator alerts the site PI and VETPALS facilitator. Because the coordinator is blind to treatment group, the site PI or VETPALS facilitator enter a secure web-based randomization scheme also maintained by Spectrum Research. The user access the website with a secure login ID and password and selects participant IDs from the electronic master screening log to obtain the treatment group. The group treatment allocation will be automatically matched to the study IDs in the system. The randomization technique will allow for a random distribution without providing any discernible pattern. Each site PI will also maintain a separate randomization log containing study IDs, name, and randomization group. This log will be in a password protected file, in a restricted access folder, on the VA network behind the VA firewall. Only the site PI and VETPALS facilitator have access to this file.
- Data from each eCRF is stored into a secure database electronically using the web-application provided by Spectrum Research. Study coordinators will have the ability to log into this web-application with their designated log-in credentials. Once the coordinator has logged in, the ability to enter participant data into a variety of web-forms becomes available. The coordinator will not have the ability to edit or view data

that has been entered from another VA site, and user-privileges will be assigned to limit or advance the abilities of the coordinator. Without a proper username and password there is no ability to view/edit any of the study data.

- Coded research data obtained from the eCRFs will be stored through SSL database encryption, behind local and master firewalls hosted by Heroku, and encrypted if necessary. Again, data will only be accessible with a valid and confirmed user ID and password. Each user ID will be assigned viewing/editing privileges based on the needs of that user, allowing or disallowing the viewing/editing of select data.

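### Staff who know every past allocation at their site may help recruit the next cohort, whose arm may be partly predictable, so concealment during recruitment is not assured

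*Combined protocol and SAP*

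**What the plan says.** Section 5.0 (Resources and Personnel) makes the blinded site coordinator the main recruiter but adds two permissions: "VETPALS facilitators may assist with screening and enrollment at their site" and "Site Principal Investigators may also assist with screening and enrollment as needed at their site".

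The same two roles sit on the allocation side:
- The facilitator's duties in section 5.0 include requesting randomization, "maintaining an accurate randomization log, and conducting the 5 intervention sessions per group of 8 ± 2 participants".
- Section 5.1 (Study Design, Randomization): "Clinical research staff at each location (site PIs and VETPALS facilitators) will receive the treatment allocation and proceed with study related activities for both conditions".
- Section 8.0 (Privacy and Confidentiality), on the site's randomization log: "Only the site PI and VETPALS facilitator have access to this file".
- Section 8.0, web route: the site PI or facilitator "selects participant IDs from the electronic master screening log to obtain the treatment group". Section 5.1 instead describes an e-mail from the facilitator or site PI to the data manager: "The email will also include a list of study ID numbers but will not contain any information that could identify participants".

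On the sequence, section 5.1 specifies 1:1 allocation of whole cohorts and says "A balanced number of groups will be randomly assigned to each site based on the projected enrollment at that site". Section 5.6 (Statistical Power) also has the arms split evenly by cohort. No block size or algorithm is given, and section 5.1 withholds both the schedule and the algorithm from sites. It concludes that the arm is hidden while each cohort is being recruited.

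**The concern.** In a trial that randomizes whole cohorts, a recruiter who can guess the next arm can influence who enters it, deliberately or not. Keeping the list secret stops anyone reading the next entry. It does not stop inference from earlier entries when the sequence is constrained to balance and the recruiter holds the site's full history.

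Here the history-holders may recruit, and the facilitator also delivers the intervention. At stake is the comparability of the arms on characteristics that were not measured, and whether the final report can claim concealed allocation without qualification.

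**Working it through.** **1. Roles side by side**

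| Step | Who does it | Knows past arms? |
|---|---|---|
| Main screening and consent (5.0, 5.1, 5.3) | Coordinator | No |
| Back-up screening and enrolment (5.0) | Facilitator, site PI | Yes |
| Back-up consent (5.3) | Another approved investigator | Possibly |
| Signal that a group has completed baseline (8.0) | Coordinator | No |
| Sending or selecting the IDs (5.1, 8.0) | Facilitator or site PI | Yes |
| Receiving the arm and keeping the log (5.1, 8.0) | Facilitator, site PI | Yes |

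The overlap is in the second row, with a possible further overlap in the third. The fifth row matters because nothing says that the list is fixed before it reaches these staff.

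**2. Number of cohorts**

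Table 1 (section 5.2) gives Seattle 12, Cleveland 12, Houston 15, Tampa 12 and Minneapolis 8. The total is 59. At 8 enrolled and 6 completing per cohort, 59 × 8 = 472 and 59 × 6 = 354, which reproduces the plan's enrolment and retention figures. Section 5.6 uses 51 cohorts, which equals 59 − 8, that is, Table 1 without Minneapolis.

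**3. Predictability with exact balance within site and no smaller blocks**

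Suppose a and b cohorts remain for the two arms. The best guess is the arm with more remaining. The expected number of correct guesses is

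C(a,b) = max(a,b)/(a+b) + [a/(a+b)]·C(a−1,b) + [b/(a+b)]·C(a,b−1), with C(0,0) = 0.

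For an even split of n = 2m this equals m − 1/2 + 2^(2m−1)/(2m choose m).

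- 8 cohorts: 4 − 0.5 + 128/70 = 5.329; 5.329/8 = 66.6%
- 12 cohorts: 6 − 0.5 + 2048/924 = 7.716; 7.716/12 = 64.3%
- 15 cohorts, split 7:8, by the recursion: 9.546; 9.546/15 = 63.6%
- All 59: (3 × 7.716 + 9.546 + 5.329)/59 = 38.02/59 = 64.4%
- The 51 without Minneapolis: (38.02 − 5.33)/51 = 64.1%

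This takes the site's list length as known and, for Houston, which arm has the extra cohort.

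**4. Other schemes compatible with the wording (assumptions, since none is stated)**

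| Scheme | Correct guesses |
|---|---|
| Permuted blocks of 2 within site | 1.5/2 = 75.0% |
| Permuted blocks of 4 within site | 2.833/4 = 70.8% |
| Permuted blocks of 6 within site | 4.1/6 = 68.3% |
| Mixed 2/4 blocks, sizes unknown (simulated) | about 71% |
| Mixed 4/6 blocks, sizes unknown (simulated) | about 67% to 68% |
| Balance over all 59 only, guessing from own site's history (simulated) | 51.5% |
| Simple randomization | 50% |

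The mixed-block rows come from 40,000 simulated sequences for each site size, and the overall-balance row from 20,000.

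**The case against.** There is a serious case for the plan.

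- **Recruitment is mainly blinded.** All eligible amputees are to be invited, the coordinator conducts screening and consent, and site PIs help only as needed. This stands, and it limits the exposure to back-up recruitment.
- **Unblinded staff do not declare a cohort ready.** A reader might infer that the facilitator decides when a group of 6 to 10 closes. Section 8.0 says that the coordinator alerts the site PI and facilitator once baselines are complete, so that reading is not supported.
- **ID selection may be clerical.** A reader might infer a free choice of members from the word used in section 8.0. The Abstract and section 5.1 place participants sequentially into successive cohorts, and the data manager checks the list and the baselines before allocating. What remains is that no text locks the list in enrolment order.
- **The algorithm is unknown.** The sentence on balance is loosely worded, and section 8.0 promises a sequence with no visible pattern. If balance is only overall, guessing is barely better than chance. This stands as the lower end of the range, although tying balance to each site's projected enrolment makes balance within site the more natural reading.
- **Certainty about late cohorts.** Under the exact-balance model, an average of 3 × 12/7 + 16/9 + 8/5 = 8.5 of 59 cohorts would be fully determined in advance. It is tempting to report that as a property of this trial. It requires sites to know their exact list length, whereas Table 1 is a projection with Minneapolis Year 4 undecided, section 5.6 uses 51 cohorts, and enrolment may reach 750.
- **The analysis offers some protection.** The outcome is change from baseline, and section 5.6 allows covariate adjustment. This reduces the effect of steering on baseline level or measured traits. It does not address unmeasured traits that predict improvement.

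**Conclusion.** The concern holds in limited form. The plan permits staff who know past allocations to recruit, and it leaves the next arm possibly predictable: about 64% to 67% correct with exact balance within site, up to 75% with small permuted blocks, and about 51.5% with overall balance only. The range depends on an algorithm that the documents do not state. Concealment during recruitment is therefore not assured whenever the permitted back-up recruitment is used.

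A reader might want to turn the guess rate into a bias in standard deviations. The documents do not support any such figure. They give neither the share of participants recruited by unblinded staff nor how far such staff could shift prognosis, and they offer no link from prognosis to the change-score outcomes. Nor do they show that steering is intended or likely. The point is a gap in safeguards that is cheap to close, and it leaves the sample size of 472 unchanged.

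**What to change.** 1. In section 5.0, delete the two permissions, so that nobody with access to allocations screens or enrols.
2. In section 5.3, restrict the investigator who may obtain consent in the coordinator's absence to someone without that access.
3. In sections 5.1 and 8.0, state that the blinded coordinator locks the cohort's ID list in consecutive order of enrolment before randomization is requested, and that the facilitator or site PI only forwards it.
4. Reconcile the e-mail route in section 5.1 with the web route in section 8.0, so that one procedure with the locked list applies.

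Varying the block sizes is not a substitute. On the measure used here, mixed small blocks are more predictable (about 67% to 71%) than one balanced list per site (64.4%). Separating the roles is what removes the problem: a recruiter with no history can guess only at 50%.

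The cost is a wording change and slightly less flexible recruitment cover when the coordinator is away. The telephone cover by Seattle staff in section 5.5 extends to baseline, record review and follow-up, not to screening or consent, so it cannot be counted on to fill that gap as written.

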6.0 Study Procedures

5.1 Study Design

Study Overview

All Veterans undergoing lower extremity amputation or receiving post-operative amputee care in the VA health care system during a 3 year period of prospective enrollment will be screened for study participation at all sites. Research staff at each site will identify potential participants who meet study eligibility criteria immediately following amputation surgery. All lower extremity amputees meeting study criteria who present to each study site will be invited to participate. All patients being considered or who have recently had lower extremity amputations are seen during the weekly amputee multidisciplinary rounds at each site. Study site coordinators and site PIs designated specifically for this study have established relationships with medical residents, fellows, physicians, and staff in various medical specialties (orthopaedics, vascular, podiatry, rehab, wound/skin) who have contact with potential participants. These personnel will refer patients to the study coordinator for evaluation of eligibility. Coordinators will also screen medical records of individuals receiving amputation in the 2 years prior to the start of the study to identify additional participants. Clinicians from one of these service lines will then introduce the study and the study coordinator to potentially eligible participants. Upon agreement from the patient, study site coordinators will approach patients individually and inquire about their interest and eligibility in volunteering for this study. Study coordinators will also mail an approach letter to patients who do not have an upcoming clinic appointment or who cannot be approached in person. Patients can call for more information or to opt-out of the study. Study coordinators will call patients who do not respond to the letter to see if they have questions or would like more information about the study.

The site study coordinator will conduct the screening interview, which includes a series of questions to confirm eligibility (screening questions), a description of the study, its importance in amputee patient care, the responsibilities of participating in the study, and the potential risks and benefits of participating. Upon patient agreement, the study coordinator will initiate the informed consent process and inform the patient of the timeline for completing the baseline questionnaire, and assign the patient a unique study ID.

Once 8±2 participants are enrolled or nearly enrolled at each site, study coordinators will schedule appointments to complete the baseline assessment, either in person or by phone. Data are collected via electronic Case Report Form (eCRF). Individual or groups of participants may attend an in-person appointment with the study coordinator either in a private room in the Clinical Research Unit or office, or in the VA library or computer lab. Participants will use computers to complete the eCRFs and study coordinators are available to help guide participants and answer any questions.

Enrolled participants are assigned on a rolling basis into successive cohorts of 8±2 individuals at each participating site. Each time 8±2 participants are enrolled, that cohort will be randomized 1:1 to receive either the VETPALS intervention or individual education support program (control condition). We will ensure that participants will not have completed a PALS program prior to study participation and will not be part of an existing PALS group during their study participation. Randomization will occur through an email exchange between the study sites (VETPALS facilitator or site PI) and the data manager at Spectrum Research. The data manager will maintain a randomization table that is stored locally on a server at Spectrum Research. When a cohort is ready for randomization, the facilitator or site PI will send an email to the data manager stating that a group of participants is ready for randomization. The email will also include a list of study ID numbers but will not contain any information that could identify participants. Within 12-24 hours of receiving the email, the data manager will verify the list of study IDs in the database to ensure all baseline assessments are complete, and then will obtain random assignment by accessing the randomization table. The data manager will respond via email to the facilitator or site PI with a value of 0 or 1 (0=individual education support program, 1=VETPALS). Both parties will retain a copy of the email for reference. The data manager will record the treatment assignment for the group in the randomization table, and the facilitator or site PI will record the treatment assignment in the randomization log. This method will ensure that treatment allocation is concealed during the recruitment of each cohort. A balanced number of groups will be randomly assigned to each site based on the projected enrollment at that site, which is a common randomization schedule used in group-based interventions. The randomization schedule and algorithm will not be shared with local sites to maintain concealment of treatment allocation. Additionally, the data manager will record a value of 0 or 1 to each study ID in the database which is linked to the study ID assigned at enrollment. Clinical research staff at each location (applicable investigators and VETPALS facilitators) will receive the treatment allocation and randomization ID in order to proceed with the treatment, intervention or control. Site study coordinators who conduct the baseline and follow-up assessments are blind to treatment.

Additionally, each VA site will partner with another VA site treating Veteran amputee patients. Providers at the partner sites (e.g. Seattle partners with Tucson) will introduce the study to potentially eligible patients. Providers will give interested patients a study brochure so that patients can contact the VA site study coordinator. Patients will be screened via telephone script and those interested and eligible in participating will be consented by telephone and mail. Coordinators will mail a research study consent form using a USPS tracking number, establish telephone contact with the patient to answer questions during the informed consent process, and provide a postage-paid envelope for the patient to return the consent form. Patients participating in this study at partner sites will participate in the study via telephone assessments

with a site study coordinator. Patients from partner sites who are randomized to the intervention group can participate via telehealth (video teleconferencing). Similarly, patients randomized to the control group are contacted by telephone and receive post-amputation education materials by mail. Providers at the partner sites assist with scheduling the VETPALS classes as usual clinical care appointments, but are not involved in interacting with the participant for research purposes.

Cohorts allocated to the intervention will work with the VETPALS facilitator and 5 clinical appointments will be created in the participant’s medical record. Participants may receive reminder phone calls prior to each scheduled session. As in the original PALS intervention, participants will be encouraged to become members of the Amputee Coalition (free of charge) which allows access to publications and educational materials. Participants also receive copies of some educational materials from the Amputee Coalition, along with a VETPALS participant workbook. The VETPALS workbook is a modified version of the original PALS workbook. The PALS workbook is publicly available by request through the Amputee Coalition of America. The VETPALS workbook has been condensed as the original PALS program was 10 weeks, and VETPALS is 5 weeks. The VETPALS intervention occurs over 5 sessions and is co-led by an allied health professional (facilitator) and a peer who is an amputee. At all sites, the VETPALS facilitator is the Amputation Rehabilitation Coordinator (ARC) of each facility and are licensed physical therapists, with advanced DOD training and certification in amputation care. Additionally, one of the sites has a second facilitator who is a Clinical Health Psychologist with a focus in physical medicine and rehabilitation. Other research staff who are trained in VETPALS (e.g. Site PIs, Co-Is) who are trained in the VETPALS intervention may lead sessions in the event of a facilitator absence. Upon completion of the study protocol, all Veterans in the VETPALS program will be offered the individual education support program.

Outline of VETPALS intervention classes

Session 1: 4 hour workshop
	
Self-management skills
 
 -Knowledge of self-management -Problem-solving -Goal-setting -Self-monitoring -Skill focus: relaxation, calming mind & body 
Tools for self-management
 
 -Communication -Relaxation

Session 2: 2 hour class
	
Managing Emotions
 
 -Knowledge of behavioral activation -Skills: building resilience and positive mood

Session 3: 2 hour class	Health and Activity -Chronic disease management knowledge -Health behaviors
Session 4: 2 hour class	Interacting with family & friends
Session 5: 2 hour class	Maintenance of self-management behaviors -Set goals for the future -Maintaining everyday life/health self-management activities -Prevention relapse

The cohorts assigned to the individual education support program (control) will be informed of their treatment group by research personnel other than the study coordinator. Participants will have access to all of the medical and rehabilitation services they would typically receive in the normal course of amputation care (e.g. post-surgical follow-up, medical stabilization and wound healing, rehab for functional independence, prosthetic fit, gait training). This includes other VA Amputation System of Care resources such as caregiver and amputee support group. Participants will not receive the VETPALS or original PALS intervention during their time in the study. To enhance usual care and encourage study participation, participants in the control condition will be systematically contacted by a clinical member of the research team and provided with post-amputation education materials. We will use one or more of the following: *First Step – A Guide for Adapting to Limb Loss* and *SideStep – A Guide to Preventing and Managing Diabetes and Its Complications* published by the Amputee Coalition and *The Next Step – The Rehabilitation Journey After Lower Limb Amputation*, a VA/DOD publication. Participants will receive a subsequent call confirming receipt of the patient education materials, and inquiring about questions associated with the information. Individuals who express an interest in additional information will be referred to their amputation care team for appropriate follow-up. All contact in the control condition will take place on an individual basis. Upon completion of the study protocol, all Veterans in the individual education support program will be offered the VETPALS program.

Participants will complete follow-up assessments with study coordinators in-person or by telephone at 6 weeks and 6 months. Study coordinators will screen for any anticipated and unanticipated adverse events at scheduled follow-up visits and by telephone contact with participants at 3 weeks and 18 weeks. Coordinators will briefly call participants to check-in, do a few medical review questions, and give a reminder of the next study appointment. Coordinators who cannot reach participants by phone at 3 or 18 weeks for the medical review questions should alert another site researcher who can complete the assessment by medical record review in CPRS. At the end of the study, coordinators will conduct a final 1-year medical record review. Study coordinators do not access the medical record until all follow-ups are complete at the end of the study in order remain blind to intervention assignment.

[figure not shown]
Additional details of the assessments and a study flow sheet can be found in the protocol document. Participants will receive reminders via telephone and mail for upcoming study visits from the study coordinator. The baseline assessment will take up to 60 minutes to complete and follow-up assessments will take up to 30 minutes to complete. Study coordinators remain blinded to treatment condition throughout the entire study and will be trained to ensure consistent and optimal administration of the assessments, as well as on strategies to remain blinded from treatment (e.g. strategies to remind patients not to reveal treatment).

Randomization

As described on page 21, this is a two-arm randomized controlled trial. The treatment allocation will automatically be matched to the study ID in the online randomization system. Clinical research staff at each location (site PIs and VETPALS facilitators) will receive the treatment allocation and proceed with study related activities for both conditions. Again, site study coordinators who conduct the baseline and follow-up assessments are blind to treatment.

This online randomization system (maintained by Spectrum Research) will have layers of security, including a requirement for a username and password to avoid intentional tampering with the treatment allocation, as well as the highest level of encryption of user information and storage into a secure SQL-based database. The system will maintain a log of all coordinators or study personnel (who have privileges) who have logged in with a time stamp. Data will be maintained in such a way that reports can be produced routinely that allow the investigators to review the treatment allocations per site. Each Site PI will also maintain a separate randomization log and patient selection log by study ID.

Participant Flow Chart

Potential Risk/Benefit Analysis

Risks to all participants: This project poses minimal risks to participants. Participants may find it inconvenient to schedule and attend appointments for the baseline, 6-week, and 6-month study interviews, which take up to one hour to complete. Participants may also feel uncomfortable about having the group assignment chosen randomly, but to minimize this risk of discomfort, all potential participants are informed that they have access to the other program once they complete the program that they are randomized to, including the follow-up assessments. The questionnaires also ask sensitive questions about physical and emotional health. Participants may be uncomfortable answering some questions. During the consent process and before each interview, participants are reminded that they can pass on any questions they do not comfortable answering. There is a risk of loss of confidentiality; although we make every effort to keep research information safe and secure, no system for protecting information can be completely secure. Finally, the study may have risks that are currently unforeseeable, but we will contact participants if new findings occur that pose a risk.

Additional risks to participants in the intervention condition: Participants may find it inconvenient to attend the VETPALS intervention sessions as the first session is 4 hours, and remaining sessions 2-5 are all 2 hours in length. Participants may also feel shy and/or

uncomfortable when participating in group discussion and other activities during the intervention sessions.

Risks to participants in the control condition: Participants in the control group may feel some discomfort or sadness about being randomized to the control/individual education support program. Participants may also feel some discomfort, sadness, or anxiety when reading post-amputation education materials, or when receiving a phone call from a researcher/clinician to confirm receipt of the materials and inquire about further questions. All Veterans in the control condition are offered the VETPALS intervention upon completion of the study protocol. This ethically ensures that study participation does not deprive Veterans of a potentially valuable service.

Anticipated benefits to society:

The VETPALS intervention is a potentially valuable health care service. This project is important to test the hypothesis that a group-based self-management intervention provides benefits above and beyond exposure to usual care and supplemental information alone in the five areas of: knowledge, problem solving, self-monitoring, behavioral goal setting, and skill acquisition. This study represents one of the only prospective randomized controlled trials of a behavioral intervention for individuals with limb loss. At the completion of the study, it is expected that the results will be used to inform the integration of self-management interventions into the VA Amputation System of Care.

Anticipated benefits to participants:

Previous research showed that the original PALS intervention improved physical and psychosocial functioning when delivered in existing community-based support groups for amputees. Other benefits of PALS include decreased isolation, greater optimism, improved knowledge of treatment and coping options, perceived coping ability, and functional social support. The PALS intervention was well tolerated in previous studies as indicated by a 90% or greater retention rate. VETPALS is an adaption of this empirically-supported self-management program.

Activities to minimize risk: Only the IRB-approved research staff will have access to research records. Patients screened for the study will be assigned a unique screening ID code, which will be linked to the last initial and full SSN (CPRS medical record). This log will be stored in a password-protected Excel file, on a secure VA network drive, in a restricted-access folder, behind the VA firewall that only the research staff has access to.

With respect to privacy and confidentiality, all enrolled participants will be assigned a unique study ID. All research data (which does not contain any PHI) will be stored entirely separate from research materials that contain PHI, such as a consent form, contact log, and consent enrollment log. The crosswalk document, which links the study ID to the patient's identity, will be maintained also in a password-protected Excel file, on a secure VA network drive, in a restricted-access folder, behind the VA firewall that only the research staff has access to.

The presence of study related adverse events will be regularly reviewed by the investigator team. The occurrence of 5 or more adverse events or 2 or more serious adverse events in either condition will trigger a review of the protocols at the time of occurrence. This process will serve several purposes. First, it will better accommodate the expected low-base rate of problems and allow for the early identification of issues than would a DSMB that met at an arbitrary regular interval.

